Training of all Study Personnel in the Responsible Conduct of Human Studies: Prior to recruiting subjects or handling study data, all study personnel will be required to pass the NIH approved course that reviews regulatory and informational documents on human subject protection and the responsible conduct of human studies. In addition, all study personnel will sign a statement of commitment to the protection of the rights and welfare of human subjects participating in research.

DATA SAFETY MONITORING PLAN

Overview: The PI will be responsible for monitoring safety throughout the trial and adhering to all reporting requirements. The PI will assume responsibility for reporting all adverse events that may arise to the IRB and/or federal funding agency, as required. Adverse events will be defined according to FDA's definition (i.e., any untoward consequence to study participants that may be related or possibly related to study procedures). Events may include, but are not limited to, worsening of psychiatric, emotional or physical symptoms; breaches in participant confidentiality, deviations from IRB-approved protocols (e.g., contacting participants to obtain survey data outside of IRB-approved time windows), or any participant safety concerns. Study recruitment, enrollment, and retention will be reviewed by the PI and research assistant (RA) weekly. Informed consents will also be reviewed weekly by the RA and PI, and monthly by the PI's mentors for the purposes of quality control. The RA will report on any issues or obstacles in recruitment, enrollment, survey administration, biospecimen collection, e-cigarette provision, and follow-up to the PI during weekly research team meetings. The RA will review all questionnaire and collected biospecimens (e.g., breath, urine) in real time to ensure data completion.

Safety monitoring plan: In this proposal, we will provide e-cigarettes to individuals who smoke cigarettes who are not ready to quit smoking. We will collect safety information related to the following categories: (1) worsening of respiratory symptoms, (2) symptoms of nicotine toxicity, and (3) adverse events of e-cigarettes previously reported to the FDA. This includes regular monitoring (every 2 weeks for all participants and more if needed determined on a case-by-case basis) of dyspnea and open-ended questions on any medical care (including hospitalizations or emergency room visits) since the last visit assessed at each study visit. While nicotine toxicity is rare in clinical trials, we will monitor breath CO levels at each study visit and also monitor for potential signs and symptoms of nicotine withdrawal. Adverse events related to e-cigarettes previously reported to the FDA include serious events such as hospitalization for pulmonary or cardiac causes, seizure, burns caused by e-cigarette devices/malfunction, and other adverse events such as headache, nausea/vomiting, dizziness, confusion, blurry vision, throat irritation, abdominal pain, and sleepiness. We will advise participants to stop e-cigarette use if necessary. A trained RA will collect all data. In the event of any adverse or other events that require immediate medical, psychiatric or other professional

intervention, the RA will immediately page the PI who will triage the patient to the appropriate emergency services (e.g., 911 or emergency room).

Attribution of adverse events: Adverse events are any side effect that occurs in a participant, while serious adverse events are those that are life-threatening, resulting in hospitalization, disability, or death. We will attribute adverse events that arise in the study to e-cigarettes according to the following scale: definite (clearly related to e-cigarettes), probable (likely related to e-cigarettes), possible (may be related to e-cigarettes), unlikely (likely not related to e-cigarettes), and unrelated (clearly not related to e-cigarettes).

Reporting of adverse events: We will report all adverse events to the Mass General Brigham (MGB) IRB and the NIH funding agency. We will also report serious adverse events, and any events requiring the trial to be stopped, to the FDA. Any complications that are deemed to be related to the study will be immediately reported to the study PI (within 24 hours). Any serious adverse events that arise throughout the course of the award period will be reported to the Mass General Brigham IRB submitted within 5 working days/7 calendar days of the date the investigator first becomes aware of the problem. All adverse events will be submitted annually for review by the MGB IRB.

11. Data and Research Material Sharing

A) Sending Data/Materials to Research Collaborators outside Mass General Brigham

Data, materials and personally identifying data will not be shared outside Mass General Brigham. The UMass Boston PI and research assistants have a non-employee research status at MGH and will work within the password protected encrypted network drive on MGH's secure server.

Receiving Data/Materials from Research Collaborators outside Mass General Brigham

De-identified data for the biomarker analysis will be received from the Mayo clinic, where the urine biomarkers will be analyzed. Mayo clinic will not be able to re-identify participants. Data will be transferred using an encrypted e-mail.

12. Privacy and Confidentiality

- Study procedures will be conducted in a private setting.
- Only data and/or specimens necessary for the conduct of the study will be collected.

- Data collected (paper and/or electronic) will be maintained in a secure location with appropriate protections such as password protection, encryption, physical security measures (locked files/areas)
- Specimens collected will be maintained in a secure location with appropriate protections (e.g. locked storage spaces, laboratory areas)
- Data and specimens will only be shared with individuals who are members of the IRB-approved research team or approved for sharing as described in this IRB protocol.
- Data and/or specimens requiring transportation from one location or electronic space to another will be transported only in a secure manner (e.g. encrypted files, password protection, using chain-of-custody procedures, etc.)
- All electronic communication with participants will comply with Mass General Brigham secure communication policies.

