Selection and provision of electronic cigarettes: Participants will receive a two-week supply of the NJOY ACE e-cigarette (NJOY, LLC). This product was selected because it is a 4th generation nicotine salt-based pod EC and is a commercially available consumer product that was granted a Premarket Tobacco Product Authorization (PMTA) from the FDA's Center for Tobacco Products (CTP) in 2022. This authorization required that FDA CTP decide that the product met the standard of being "appropriate for the protection of the public health," defined as it having net public health benefits that exceed its net public health risks. A tobacco product with a PMTA designation is not considered by FDA CTP to be an investigational device and does not need to obtain certification from the CTP's Investigational Tobacco Products (ITP) Program when it is used in a research study. We have confirmed the accuracy of this statement with an email communication with [name] of the FDA CTP's IPT Program (dated July 11, 2024).

The NJOY ACE contains a device and sealed pods available with 5% nicotine and is tobacco flavored. Each pod is equivalent to ~20 cigarettes, and participants will receive an EC pod supply equivalent to their average cigarette smoking rate at baseline. The supply of pods provided will be adjusted as needed to ensure the adequate amount to substitute cigarette use.

Participants will receive written and verbal instructions on how to use the device and be provided with written educational materials used in previous research trials to help vapers quit smoking. They will be instructed to use the EC instead of their usual CC brand, encouraged to switch completely to the EC by the end of the first week and try to use only the EC for the rest of EC provision period. All devices and pods will be labeled for investigational use only. Dispensing and collection logs will be used to track devices and pods. We will collect and count used and unused pods at visits.

Schedule of Assessments:

- a) Initial Phone Screening: Telephone screening will determine initial eligibility. Initial screening will query on all inclusion and exclusion criteria, except for CO. For those who meet the initial eligibility criteria, a research assistant (RA) will explain the purpose and procedures of the study, provide information on confidentiality, answer questions, and invite participant for an in-person final eligibility visit.

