- b) Baseline visit (Consent, Final eligibility, baseline data collection and product provision): Participants will receive a study overview. Informed consent for the study will be obtained. Final in-person eligibility will be confirmed with an exhaled carbon monoxide via Bedfont Micro Smokerlyzer. Participants meeting final eligibility will be enrolled in the study. Baseline data collection will immediately follow screening at the same visit. Measures will be completed per the schedule of measures above (see Table 1), broadly including: recent CC and EC use, cigarette dependence; respiratory symptoms; intentions to quit smoking; and biomarkers of tobacco use and inflammation. Biological assessments involving urine sample collection will be performed by the RA.
Following completion of all scheduled measures, participants will be provided with a complimentary NJOY ACE device, information on its storage and use, and disposable cartridges in the tobacco flavor. Participants will be provided with a number of pods comparable to 150% of their weekly consumption of nicotine based on their responses to the baseline timeline follow-back (TLFB). This quantity will ensure that participants have adequate pods to fully substitute combustible cigarettes within a reasonable margin of error (e.g., timing/scheduling of the next session) should they choose to do so. As each standard 5% NJOY ACE pod provide an amount of serum nicotine delivery in ideal use conditions comparable to one pack of cigarettes (i.e., 20 cigarettes), we will compute participants' average weekly cigarette consumption in packs and provide 1.5x that number of cartridges.
- c) Phone call visits at Weeks 1 and 3: These visits will be conducted by phone. Participants will be assessed for their cigarette, tobacco, and EC use. Participants will also be assessed for any quit attempt or adverse event and will be asked for any issues using the product and reminded to use the EC instead of the CC every time they want to smoke.
- d) In person Visit at Week 2: Participants will attend an in-person visit at Week 2 to receive a new 2-week supply of pods, return used and unused pods to measure EC use, complete assessments and troubleshoot device or other study-related issues.
- e) In person Visit at Week 4: Participants will attend an in-person visit at Week 4 when product provision will end and all baseline assessments will be repeated.

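### The baseline pod formula (1.5 times one week's packs) covers 10.5 days of full substitution, but the supply must last two weeks

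*Combined protocol and SAP*

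**What the plan says.** All the relevant text is in section 6 (Study Procedures).

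- Under Selection and provision of electronic cigarettes: "Participants will receive a two-week supply of the NJOY ACE e-cigarette (NJOY, LLC". That subsection equates a pod with about 20 cigarettes and says "participants will receive an EC pod supply equivalent to their average cigarette smoking rate at baseline". It adds: "The supply of pods provided will be adjusted as needed to ensure the adequate amount to substitute cigarette use". Participants are "encouraged to switch completely to the EC by the end of the first week".
- Under Schedule of Assessments, item b (baseline visit), the quantity is described as 150% of weekly consumption and then as an operating rule: "we will compute participants' average weekly cigarette consumption in packs and provide 1.5x that number of cartridges". Its purpose is also stated: "This quantity will ensure that participants have adequate pods to fully substitute combustible cigarettes within a reasonable margin of error", with the timing of the next session given as an example of what the margin is for.
- Under item c, Weeks 1 and 3 are phone contacts at which participants "will be asked for any issues using the product". No dispensing is described.
- Under item d: "Participants will attend an in-person visit at Week 2 to receive a new 2-week supply of pods".

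No rule for rounding to whole pods is given.

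**The concern.** A weekly quantity is applied to a two-week interval. A participant who switches completely and early, which is the behaviour the trial encourages, could run out of pods before Week 2, although item b says the quantity guards against exactly that.

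For anyone who runs out, the Week 2 pod count is capped by supply. That count matters because the Quantitative measures list says the amount of e-cigarette use will otherwise not be quantified. A return to cigarettes before the visit is possible, though not certain. It would show in Week 2 cigarettes per day (CPD), breath CO and urine markers. Week 2 CPD and CO also enter the linear mixed models in section 9. The study is meant to inform a larger randomized trial, so the dispensing rule may be reused.

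**Working it through.** **Inputs.** One pod = 20 cigarettes (section 6). Baseline pods = 1.5 x weekly packs (item b). Next dispensing at day 14 (item d). Minimum 5 CPD, or 35 cigarettes a week (section 4). Planning data: 14.8 CPD falling to 4.4 (section 9, Power).

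**Plan's own figure.** The stated supply is 14 days. Let W = CPD x 7/20, the weekly packs. Pods supplied = 1.5W. Days of full substitution = pods x 20/CPD = 1.5 x 7 = **10.5**, whatever the CPD. Fourteen days needs 2.0W. The shortfall is 3.5 days, or 3.5/14 = 25%. The stated two weeks are not reproduced.

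**Rounding up to whole pods.** The last column assumes a linear rise from no substitution to full substitution by day 7. That uses 3.5 days' worth of pods in week 1, so the supply ends on day (days covered + 3.5).

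| CPD | 1.5W | Pods, rounded up | Days covered | Pods for 14 days (2.0W, rounded up) | Last day on the ramp |
|---|---|---|---|---|---|
| 5 | 2.625 | 3 | 12.0 | 4 | 15.5 |
| 10 | 5.25 | 6 | 12.0 | 7 | 15.5 |
| 14.8 | 7.77 | 8 | 10.8 | 11 | 14.3 |
| 20 | 10.5 | 11 | 11.0 | 14 | 14.5 |
| 30 | 15.75 | 16 | 10.7 | 21 | 14.2 |

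Over every whole weekly total from 35 to 280 cigarettes (5 to 40 CPD), days covered run from 10.5 (40 a week) to 13.66 (41 a week). None reaches 14. This holds in general:

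- For W of 2 or more, the rounded-up count is below 1.5W + 1, which is at most 2W.
- For W from 1.75 to 2, the count is 3, while 2W is at least 3.5.

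Rounded down, whole-number rates of 5 to 30 CPD give 8.0 to 10.5 days.

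**Gradual switching.** On the linear ramp the unrounded supply ends on day 10.5 + 3.5 = 14.0, with no margin. Rounded up, a Week 2 visit one day late (day 15) falls after the supply ends at 14.8, 20 or 30 CPD.

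**Average switching.** The planning reduction is (14.8 - 4.4)/14.8 = 0.703. If pod use tracks cigarettes replaced, the unrounded supply lasts 10.5/0.703 = 14.9 days.

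**The case against.** The strongest reply is that 150% was meant as a weekly rate, supplied for each of the two weeks: 3.0 times weekly packs, or 21 days. That would fit both the two-week description and the stated margin, and it may be what was intended. But the operating sentence multiplies one week's packs by 1.5 and stops there, so the text would still need correcting. The statement that supply matches the baseline smoking rate adds a third quantity: over two weeks it means 2.0 times weekly packs, or 14 days.

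Second, the protocol does not ask for full switching on day 0, and on its own schedule the shortfall nearly disappears. This stands, and it limits the consequence. What is then missing is mainly the scheduling margin.

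Third, supply may be adjusted as needed (sections 6 and 7), the Week 1 call asks about product problems, and participants may contact staff at any time. These may help individuals. However, the adjustment is unquantified and no dispensing before Week 2 is described, so the claim made for the formula itself remains untrue.

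Fourth, there are narrow exceptions to the 14-day limit. If packs are rounded up first and then pods, 41 to 50 cigarettes a week gives 14.0 to 17.1 days. The entry criterion covers the past month while pods are set from a 7-day recall, so a baseline week can fall below 35 cigarettes; at 27 to 30, 3 pods last 14.0 to 15.6 days. The text prescribes neither rounding step, and both cases lie at the low end of consumption.

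**Conclusion.** The inconsistency is real and minor. As written, the baseline rule supplies 10.5 days of full substitution for a 14-day interval. Rounding the pod count up gives at most 13.7 days for any baseline week of 35 cigarettes or more. This rests on the protocol's pod-to-pack equivalence and the literal wording of item b.

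The practical effect is limited to fast, full switchers, whose number cannot be known from the documents. It would be confined to Week 2 CPD, CO, urine and pod-count data, and to the mixed models using Week 2 CPD and CO. The primary change from baseline to Week 4 would be touched only if 1.5 times weekly packs were reused at Week 2, which the protocol does not say. Enrollment and retention are not shown to be affected.

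**What to change.** Rewrite the item b formula on the dispensing interval: at least 2.0 times average weekly packs (CPD x 14/20), rounded up to whole pods, plus a margin the investigators choose. One form is pods = CPD x (14 + d)/20, rounded up, where d is the number of days by which the Week 2 visit may be late. If a 50% margin over the full two weeks was intended, write 3.0 times weekly packs. State the same basis for the Week 2 supply, align the sentence that equates supply with smoking rate, and keep the provision for individual adjustment.

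The cost is one or two sentences and some pods. Moving from 1.5 to 2.0 times, both rounded up, adds 1 pod per participant at 5 or 10 CPD, 3 at 14.8 or 20, and 5 at 30. If all 30 participants smoked at the given rate, the totals would be 30, 90 and 150 pods. An assumed three-day margin at 14.8 CPD gives 14.8 x 17/20 = 12.58, so 13 pods: 2 more each, or 60 in all. The drawback is somewhat more unused nicotine product held at home until collection at Week 2.

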This is an open-label single-arm pilot clinical trial testing the feasibility, acceptability, and effects of a 4-week EC substitution intervention in 30 current smokers. Approach: Participants will be asked to switch from CC to the NJOY ACE electronic cigarette (EC) for 4 weeks. They will receive counseling to develop a plan to fully substitute CC for EC and to increase EC adherence. Follow-up assessment at 8 weeks will determine whether participants continue to use EC, return to cigarette smoking, or use both products. The primary outcomes are study feasibility (participant enrollment and retention) and change in cigarettes per day from baseline to week 4 (primary outcome). Secondary outcomes include change in exposure biomarkers (expired air CO, urine cotinine and anabasine) from baseline to week 4, product acceptability and tolerability (days of EC use, adverse events) and change in CC and EC use after EC provision ends. At the end of EC provision (week 4), we will conduct exploratory qualitative exit interviews in a purposive subsample to explore their experiences participating in the study and switching from CCs to ECs.

4. Subject Selection

Inclusion Criteria

- a) Participants in the Screen Assist study (IRB#2018P000539) who self-reported smoking cigarettes at the end of the study and were asked to complete a subsequent Screen Assist survey to ascertain their potential interest in a research study to test the effects of switching from CC to EC. Individuals who expressed interest in a future research study about EC on that survey are eligible for this study.
- b) Smoked ≥ 5 cigarettes/day in past month
- c) Willingness to try switching to EC for 4 weeks
- d) Own a mobile telephone
- e) Smoking status at study entry confirmed by breath carbon monoxide (CO) ≥ 6 ppm
- f) English speaking
- g) Willingness to travel to the MGH main campus for 3 in-person visits

Exclusion Criteria

- a) Plan to quit smoking and have set a quit date in the next 30 days
- b) Current EC use on >2 days in the past 30 days
- c) Hospitalization for acute coronary syndrome, unstable angina, CHF, stroke, pneumonia or COPD/asthma exacerbation in the past 1 month
- d) Be willing not to smoke marijuana in the 24h before each study visit

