6. STUDY PROCEDURES

	Phone Screening	EC Provision					F/U Phone Call
		In person screening / In Person Baseline	Phone Call	In person Visit	Phone Call	In Person Visit	
	-14	Week 0	Week 1	Week 2	Week 3	Week 4	Week 8
Screening and Enrollment							
Tobacco history since survey completion: past 30-day CC and EC use, plan to quit smoking in the next 30 days	X						
Other screening items	X						
Breath Carbon Monoxide		X					
Baseline Measures							
Current medical history		X					
Alcohol use screening		X					
CC and EC Use							
Recent CC quit attempts		X	X	X	X	X	X

Mass General Brigham Institutional Review Board
Intervention/Interaction Detailed Protocol

Current CC Use: Past 7-day use (Yes vs.no) and 7-day timeline follow back interview (TLFB)		X	X	X	X	X	X
Current EC use: Past 7-day use (Yes vs.no) and 7-day timeline follow back interview (TLFB)		X	X	X	X	X	X
EC pod collection/count				X		X	
Nicotine, CC, and EC Perceptions							
Absolute and comparative health and addiction risk perceptions of EC, CC and Nicotine		X				X	X
EC Acceptability							
E-Cigarette Sensory Effects and Appeal Ratings				X		X	
Electronic cigarette rating scale				X		X	
Electronic Cigarette Smoking Consequences Questionnaire				X		X	
Readiness to switch to EC							
Electronic cigarette taste and feel compared to cigarette				X		X	
Dependence, Withdrawal and Craving							
Time to first cigarette, number of cigarettes smoked per day; short-form PROMIS Nicotine Dependence Item Bank		X		X		X	
Penn State e-cigarette dependence index				X		X	
Minnesota Nicotine Withdrawal Scale (MNWS)		X		X		X	
Brief Questionnaire on smoking urges		X		X		X	X
Biomarkers							
Breath carbon monoxide (CO)		X		X		X	
Urine Cotinine		X		X		X	
Urine Anabasine		X		X		X	
Adverse events							
Adverse events			X	X	X	X	
Respiratory symptoms: American Thoracic Society questionnaire		X	X	X	X	X	
Exit qualitative interview							X

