i) EC Acceptability: Subjective effect of EC (e.g. satisfaction, psychological reward, craving reduction) using the modified E-Cigarette Sensory Effects and Appeal Ratings and the Electronic cigarette rating scale⁰;²⁶ beliefs and behaviors related to EC measuring nine positive expectancies and seven negative expectancies related to EC using the Electronic Cigarette Smoking Consequences Questionnaire;²⁷ Participants will also be asked to compare the taste, satisfaction and helpfulness for managing cravings of the study e-cigarette to the usual cigarette they smoked before the study.

j) Cigarette and e-cigarette dependence: Time to First Cigarette and Time to First EC of the Day measured with the Fagerstrom Test of Cigarette Dependence (FTCD);²⁸ and its e-cigarette adaptation.²⁹ Patient Reported Outcomes Measurement Information System (PROMIS) Nicotine Dependence Item Bank.^{30,31} The Penn State electronic cigarette dependence index will also be included to assess e-cigarette dependence.³³

k) Nicotine Withdrawal Symptoms: Minnesota Nicotine Withdrawal Scale (MNWS)³⁴, which assess both the desire to smoke and withdrawal symptoms.

l) Smoking Urges: Questionnaire of smoking urges-brief.³⁵

- m) **Biomarkers of Exposure:** Exhaled breath samples measured as concentration of Carbon Monoxide (CO) in parts per million. Cotinine and Anabasine measured in the urine sample. Cotinine is the major metabolite of nicotine. It is found in both CC and ECs. It will be measured to assess EC safety. Cotinine may or may not change with a CC to EC switch, depending on degree of substitution.³⁶ Anabasine is a tobacco alkaloid that reflects exposure to combustible tobacco products and should fall with reductions in CPD.³⁶ Urine samples will be collected and stored at MGH and analyzed at Mayo Clinic laboratories.
- n) **Respiratory Symptoms:** Assessed with the American Thoracic Society questionnaire.³⁷
- o) **EC Adverse Events:** self-reported adverse events with open-ended questions about new symptoms since the last visit, then symptom checklist of common vaping side effects,

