Remuneration: Remuneration will be provided via gift cards purchased on an MGB Corporate Card. Participants will receive gift cards for their participation. Participants will receive \$50 for attending the baseline in-person visit, \$50 for attending the Week 2 visit, and \$80 for attending the Week 4 in-person visit, and \$30 for a Week 8 phone visit. Participants will receive \$15 for completing the phone visits at Weeks 1 and 3. Total possible compensation is \$240. Compensation will not be contingent on EC or CC use status.

7. Risks and Discomforts

a) *E-cigarette use:*

E-cigarettes are devices that heat nicotine to produce an aerosol that users "vape." The health effects of e-cigarettes are still unclear, but preliminary data suggest that using e-cigarettes is generally less harmful than smoking tobacco cigarettes in that e-cigarettes expose users to fewer toxicants than cigarettes,¹² and emerging data suggest that smokers who switch completely from conventional cigarettes to e-cigarettes will likely reduce their risk of tobacco-related health harms (the goal of the present study). Most exclusive e-cigarette users have lower nicotine levels than when they smoked regular combustible cigarettes. Some e-cigarette users, especially those who use both e-cigarettes and regular tobacco cigarettes, as well as youth and young adults, can have increased nicotine levels, though recent data suggests that on average, exclusive vapers, exclusive cigarette smokers and dual users of both products have similar levels of daily nicotine intake.³⁸ In some rare cases, these use patterns have been associated with seizures. Whether this would occur with individuals instructed to switch completely to e-cigarettes from cigarettes is unclear but based on prior data we would hypothesize highly unlikely to occur in the present study. E-cigarette users very often maintain an addiction to nicotine, but this addiction appears to be somewhat less than that from tobacco cigarettes. Abruptly quitting e-cigarettes could cause withdrawal symptoms similar to those from quitting tobacco cigarettes but slightly less severe. The most common side effects include dry mouth, irritation of the throat and mouth, and mild cough.

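### The adverse-event checklist is not scheduled before the e-cigarette is dispensed, so pre-existing symptoms outside the respiratory and withdrawal scales may be recorded as e-cigarette adverse events

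*Combined protocol and SAP*

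**What the plan says.** Section 3 describes the design: "This is an open-label single-arm pilot clinical trial testing the feasibility, acceptability, and effects of a 4-week EC substitution intervention in 30 current smokers". Among the secondary outcomes it lists "product acceptability and tolerability (days of EC use, adverse events").

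The instrument is item o) of the quantitative measures in section 6: "open-ended questions about new symptoms since the last visit, then symptom checklist of common vaping side effects". The checklist itself is not reproduced.

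The schedule table in section 6 has seven columns: phone screening and weeks 0, 1, 2, 3, 4 and 8. Three rows matter:

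- "Adverse events X X X X": weeks 1, 2, 3 and 4.
- "Respiratory symptoms: American Thoracic Society questionnaire X X X X X": week 0 and weeks 1 to 4.
- "Minnesota Nicotine Withdrawal Scale (MNWS) X X X": weeks 0, 2 and 4.

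The baseline visit (section 6, Schedule of Assessments, item b) lists respiratory symptoms among its measures but no side-effect checklist. The device is handed over only once the scheduled measures are finished.

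Section 7 a) states: "The most common side effects include dry mouth, irritation of the throat and mouth, and mild cough". It also says that adverse events are assessed at every visit. The safety monitoring plan in section 10 lists further events previously reported to the FDA, among them headache, nausea or vomiting, dizziness, blurry vision and throat irritation. It also sets a five-level attribution scale running from definite to unrelated.

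**The concern.** With no control group, the participant's own report before exposure is the only internal comparator for a symptom reported during e-cigarette provision. The population is older, long-term smokers, who may have dry mouth or an irritated throat before they vape. If the checklist is first given at week 1, a ticked item cannot be classified from the data as new, worse or unchanged.

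Two things follow for the tolerability outcome. Symptoms that were already there may be recorded as e-cigarette adverse events. A symptom that eases after switching cannot be shown to have eased. The person assigning attribution must rely on what the participant remembers, in a trial where both know the product. The pilot is meant to inform a fully powered trial, so its tolerability figures would carry this uncertainty forward.

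**Working it through.** **The plan's own figure.** Section 9 gives no adverse-event rate, precision or test, so there is nothing of that kind to reproduce. Its one power figure concerns cigarettes per day: n = 24, d = 0.60, two-sided 5%. A paired t-test with 23 degrees of freedom and noncentrality 0.60 × √24 = 2.94 has power 0.804, which agrees with the stated 80%. The present point does not depend on it.

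**Step 1: is week 0 really blank?** The adverse-event row has four marks. The respiratory row directly below it has five, and the extra one falls at week 0. The text agrees: the baseline visit description lists respiratory symptoms and no adverse-event questions, while the description of the week 1 and week 3 calls does include adverse events. Only section 7 a) points the other way, with its statement that every visit is covered. Week 8 is also blank in that row.

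**Step 2: do other week 0 measures fill the gap?**

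| Week 0 measure | What it covers (section 6) | What it leaves open |
|---|---|---|
| ATS questionnaire | Respiratory symptoms; cough is taken to belong here | Dry mouth; throat or mouth irritation |
| MNWS | Desire to smoke and withdrawal | Side effects that are not withdrawal symptoms |
| Current medical history | Diagnoses made by a physician | Symptoms |

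Of the side effects that section 7 a) calls most common, cough is covered. Dry mouth and throat or mouth irritation are not shown to be. Any section 10 symptoms that are on the checklist and are neither respiratory nor withdrawal symptoms share the gap.

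**Step 3: could week 1 serve as baseline?** No. Participants receive the device at week 0 and are encouraged to have switched completely by the end of the first week.

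**Step 4: how large could it be?** The documents give no prevalence, so this is illustration. Let p be the assumed share of participants with a given symptom before dispensing, and q = 10% the assumed true new onset among the rest. Suppose all 30 respond and everyone with the symptom ticks it.

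- Already symptomatic = 30 × p
- Share ever ticking the item = p + (1 − p) × q
- Share of those who were symptomatic beforehand = p ÷ [p + (1 − p) × q]

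| p | Already symptomatic | Ever ticking | Pre-existing among them |
|---|---|---|---|
| 10% | 3 of 30 | 0.10 + 0.90 × 0.10 = 19% | 0.10 ÷ 0.19 = 53% |
| 20% | 6 of 30 | 0.20 + 0.80 × 0.10 = 28% | 0.20 ÷ 0.28 = 71% |
| 30% | 9 of 30 | 0.30 + 0.70 × 0.10 = 37% | 0.30 ÷ 0.37 = 81% |
| 40% | 12 of 30 | 0.40 + 0.60 × 0.10 = 46% | 0.40 ÷ 0.46 = 87% |

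Even at the low end of this range, about half of those ticking the item would have had the symptom beforehand. The last two columns depend on q as well as on everyone affected ticking; the count already symptomatic depends only on p.

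**The case against.** The strongest reply is that a ticked item is not yet an e-cigarette event. Section 10 puts an attribution step in between, and its scale includes unlikely and unrelated. A reader might infer that background symptoms will inevitably be counted against the product; the documents do not support that. What remains is that the attribution is made without a recorded starting point.

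Second, the checklist is not in the documents. Item o) can be read as one sequence in which the checklist follows the question about new symptoms and shares its time frame, and the item ends in a comma, so text may be missing. The form may well ask only about new or worsened symptoms. That stands as a real uncertainty. It would reduce false recording, but the comparison would still rest on recall, and improvement would still go unmeasured.

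Third, a reader might infer that the trial cannot separate any product effect from background. That is too broad. Respiratory and withdrawal symptoms are measured from week 0, and worsening respiratory symptoms are a named safety category. A fall in cough, for example, need not be missed. Nor do the documents say that headache, nausea or dizziness are on the checklist: these come from the section 10 list, and item o) speaks only of common vaping side effects.

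Finally, this is a 30-person feasibility pilot whose primary outcomes are enrollment, retention and change in cigarettes per day, and section 9 plans no adverse-event test. That limits the weight of the point but does not remove it.

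**Conclusion.** The point holds in limited form. The schedule has no adverse-event checklist before dispensing, and this conflicts with the statement in section 7 a) that every visit is covered. For side effects outside the respiratory and withdrawal scales, clearly dry mouth and throat or mouth irritation, pre-existing symptoms may be recorded as e-cigarette adverse events, attribution leans on recall, and improvement cannot be measured.

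The effect is on one component of a secondary outcome. No primary outcome and no stated figure changes. The size is unknown from the documents: 3 to 12 of 30 participants per symptom under an assumed prevalence of 10% to 40%. How many of these would actually be recorded as events depends on the unseen checklist wording and on how attribution is applied. The change is still worth making before enrollment, because a pre-exposure report cannot be recovered once the device is in use.

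**What to change.** 1. Add a week 0 mark to the adverse-event row for the symptom checklist, completed before the device is handed over, with the same items and wording as at weeks 1 to 4.
2. State in section 9 that checklist events at weeks 1 to 4 are summarised as new or worsened relative to week 0.
3. Make the week 0 checklist available to whoever assigns attribution under section 10.
4. Reconcile the statement in section 7 a) that every visit is covered with the schedule, which leaves weeks 0 and 8 blank.

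The cost is a few extra minutes at a baseline visit that already takes place, plus short edits to the table and to sections 7 and 9. No extra visit or sample is needed, and sample size and power are unchanged.
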